5.2 Derivation of Health Outcomes Scores

SF-36v2 Acute Recall – Calculation of Domain and Summary Index Scores

The 36 questions in the SF-36v2 questionnaire are used to evaluate patients' perception of their general quality of life in 8 areas: physical functioning, role-physical (role limitations caused by physical problems), social functioning, bodily pain, mental health, role emotional (role limitations caused by emotional problems), vitality and general perception of health.

The score for each domain is a summation of the numerical responses from a subset of the 36 questions (as shown in the table below). For questions 1, 2, 6, 7, 8, 9a, 9d, 9e, 9h, 11b and 11d low response scores indicate better health status, hence the response to these questions are re-coded in the reverse order prior to any summations. If in error, two or more responses are given for a patient for a particular question then the worst score will be used in calculating the domain score. For the questions indicated above this would be for the higher scores, and for all other questions it would be the lower scores. Any out of range values will be treated as missing.

Domain	Question	Lowest-Highest possible score	Maximum Allowed Missing Responses*
Physical Functioning	3a, 3b, 3c, 3d, 3e, 3f, 3g, 3h, 3i, 3j	10 – 30	5
Role-Physical	4a, 4b, 4c, 4d	4 – 20	2
Bodily Pain	7, 8	2 – 12	1
General Health	1, 11a, 11b, 11c, 11d	5 – 25	2
Vitality	9a, 9e, 9g, 9i	4 – 20	2
Social Functioning	6, 10	2 – 10	1
Role-Emotional	5a, 5b, 5c	3 – 15	1
Mental Health	9b, 9c, 9d, 9f, 9h	5 – 25	2

* If no. missing responses are ≤ maximum allowed, the mean of the available responses can be used to substitute for the missing values in calculation of domain score. If no. of missing values is > maximum allowed the domain score cannot be calculated.

Further details about these eight domains can be found in the manual 'SF-36 Health Survey - Manual and Interpretation Guide'.

Each domain score is converted to a 0-100 scale norm-based score (a mean of 50 and a SD of 10) based on the general U.S. population in 1998 using the following equation:

$$\text{Domain score} = \left[\frac{(\text{Actual raw score} - \text{Lowest possible raw score})}{\text{Possible raw score range}} \right] \times 100$$

This transformation converts the domain scores to a value between 0 and 100, scores between these values represent the percentage of the total possible score achieved.

Re-Scoring Responses

For all scores a linear relationship between the scores and health concept is assumed. The following scores are rescored to satisfy this assumption. Further details regarding this can be found in the SF36v2 Manual.

Bodily Pain (BP) – Questions 7 and 8

Question 7 Original Value	Question 7 New Value
1	6
2	5.4
3	4.2
4	3.1
5	2.2
6	1

Question 8 Original Value	Question 8 New Value
Q7 missing ,Q8 = 1	6
Q7 missing, Q8 = 2	4.75
Q7 missing, Q8 = 3	3.50
Q7 missing, Q8 = 4	2.25
Q7 missing, Q8 = 5	1.00
Q7 = 1, Q8 = 1	6
Q7 between 2 and 6, Q8 = 1	5
Q7 between 1 and 6, Q8 = 2	4
Q7 between 1 and 6, Q8 = 3	3
Q7 between 1 and 6, Q8 = 4	2
Q7 between 1 and 6, Q8 = 5	1

General Health Perceptions (GH) – Questions 1 and 11a – 11d

Question 1 Original Value	Question 1 New Value
1	5
2	4.4
3	3.4
4	2
5	1

Question 11b and 11d Original Value	Question 11b and 11d New Value
Any	6 – Original Value

Vitality (VT) – Questions 9a, 9e, 9g and 9i

Question 9a and 9e Original Value	Question 9a and 9e New Value
Any	6 – Original Value

Social Functioning (SF) – Questions 6 and 10

Question 6 Original Value	Question 6 New Value
Any	6 – Original Value

Mental Health (MH) – Questions 9b – 9d, 9f and 9h

Question 9d and 9h Original Value	Question 9d and 9h New Value
Any	6 – Original Value

Calculation of Component Scores

Two component scores are calculated from the 8 domain scores; the physical component summary (PCS) and the mental component summary (MCS).

First the 8 domain scores are standardized using a z-score transformation based on scores from the general US population. This gives the 8 scores PF_Z, RP_Z, BP_Z, GH_Z, VT_Z, SF_Z, RE_Z, MH_Z.

$$\text{Domain score normalised} = \frac{(\text{Domain score} - \text{Mean})}{\text{Standard deviation}}$$

Therefore:

$$\text{PF}_Z = (\text{PF} - 82.62455) / 24.43176 \quad \text{RP}_Z = (\text{RP} - 82.65109) / 26.19282$$

$$BP_Z = (BP - 73.86999) / 24.00884$$

$$VT_Z = (VT - 58.41968) / 20.87823$$

$$RE_Z = (RE - 87.50009) / 22.01216$$

$$GH_Z = (GH - 70.78372) / 21.28902$$

$$SF_Z = (SF - 85.11568) / 23.24464$$

$$MH_Z = (MH - 75.76034) / 18.04746$$

Each component score is then transformed to a norm based (mean = 50, SD = 10) score, based on the general U.S. population in 1998. This is achieved by multiplying each aggregated component scale score by 10 and adding the resulting product to 50.

$$\text{Norm based Domain score} = 50 + (\text{Normalised Domain score} * 10)$$

These scores are then aggregated using weights (factor score coefficients) which are specific to the physical and mental summary measures. The calculations are as below.

Physical Component Summary (PCS):

$$\begin{aligned} AGG_PHYS = & (PF_Z * 0.42402) + (RP_Z * 0.35119) + (BP_Z * 0.31754) \\ & + (GH_Z * 0.24954) + (VT_Z * 0.02877) + (SF_Z * -0.00753) \\ & + (RE_Z * -0.19206) + (MH_Z * -0.22069) \end{aligned}$$

Mental Component Summary (MCS):

$$\begin{aligned} AGG_MENT = & (PF_Z * -0.22999) + (RP_Z * -0.12329) + (BP_Z * -0.09731) \\ & + (GH_Z * -0.01571) + (VT_Z * 0.23534) + (SF_Z * 0.26876) \\ & + (RE_Z * 0.43407) + (MH_Z * 0.48581) \end{aligned}$$

Functional Assessment of Chronic Illness Therapy-Fatigue

A 13-item FACIT-Fatigue Scale (Version 4)

The FACIT-Fatigue Scale is stand alone subscale consisting of 13 questions. All questions within this subscale employ a 5-point response scale ranging from 0 (Not at all) to 4 (Very much). All but two of the 13 responses are reversed prior to calculating the fatigue subscale score, this reversal is done by subtracting the responses from 4.

If there are missing responses to any questions, the Fatigue subscale score can be pro-rated as long as more than 50% of the responses are present (at least 7 questions have been answered). The Fatigue subscale score is thus calculated by summing the individual item scores, multiplying by 13 (the number of items in the subscale) and dividing by the number of items actually answered.

The Fatigue subscale score has values between 1 and 52, with the higher scores indicating better quality of life.

Fact-Th6

There are 6 items. The total score is calculated by summing Th3+Th4+ Th10+ Th11 + Th12 and An7 after reversal. If there are missing responses to any questions, the Fact-Th6 subscale score can be pro-rated as long as more than 50% of the responses are present (at least 4 questions have been answered).

TSQM-9

There are three domains in TSQM-9: Effectiveness, Convenience, and Global Satisfaction. Scores for each domain are computed by adding the TSQM items in each domain and then transforming the composite score into a value ranging from 0 to 100. A score can be computed for a domain only if no more than one item is missing. The calculations specific to each domain are presented in detail below.

Global Satisfaction

$$([Sum(Item 7 to Item 9) - 3] divided by 14) * 100$$

If either Item 7 or 8 is missing

([(Sum(the two completed items)) – 2] divided by 10) * 100

If Item 9 is missing

([(Sum(Item7 and Item8)) – 2] divided by 8) * 100

Effectiveness

([(Item 1 + Item 2 + Item 3) – 3] divided by 18) * 100

If one item is missing

([(Sum(the two completed items – 2] divided by 12) * 100

Convenience

([Sum(Item 4 to Item 6) – 3] divided by 18) * 100

If one item is missing

([(Sum(the two completed items)) – 2] divided by 12) * 100

6 References

1. Oncology guideline for safety analysis, v1.0, dated 09-Jun-2016
5. Ware JE (2000) SF-36 health survey update. *Spine.* 25:24:3130-3139.

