6-item subset of the more detailed FACT-Th, which is an 18-item subscale of the validated FACT that specifically measures concerns related to thrombocytopenia in the past 7 days. The FACT-Th6 is scored using a 5-level Likert scale (0=not at all to 4=very much) and is calculated by summing scores for the 6-items; therefore, scores can range from 0–24, with higher scores representing better HRQoL. No minimum clinically important change thresholds have been established for FACT-Th6. Tentatively anchor-based methods (e.g., based on Patient Global Impression of Change [PGIC] and Patient Global Impression-Severity [PGIS]) and distribution-based methods will be used to determine meaningful change in scores. FACT-Th6 demonstrated good reliability and validity for measuring the proposed constructs in the ITP population. Patients will be administered the FACT-Th6 at baseline, every 3 months during treatment or while in sustained remission, at months 15, 18, 21, 24, and at end of treatment.

The **GP5**, which is a single question, is used to assess the overall bothersomeness of treatment side effects. The GP5 is scored using a 5-point rating scale (0 = not at all; 1 = a little bit; 2 = somewhat; 3 = quite a bit; and 4 = very much), where lower scores reflect less bothersomeness from treatment side effects. The GP5 will be evaluated at baseline and end of treatment.

Treatment Satisfaction Questionnaire for Medication (TSQM-9) will be used to assess treatment satisfaction with medication. The three scales of the TSQM-9 include the effectiveness scale, convenience scale, and global satisfaction scale. TSQM-9 will be evaluated at baseline and end of treatment.

9 Study discontinuation and completion

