				
 1	 2	 3	 4	 5

9. These questions are about how you feel and how things have been with you during the past 4 weeks. For each question, please give the one answer that comes closest to the way you have been feeling. How much of the time during the past 4 weeks...

All of the time	Most of the time	Some of the time	A little of the time	None of the time
-----------------	------------------	------------------	----------------------	------------------

a Did you feel full of life? 1 2 3 4 5

b Have you been very nervous? 1 2 3 4 5

c Have you felt so down in the dumps that nothing could cheer you up? 1 2 3 4 5

d Have you felt calm and peaceful? 1 2 3 4 5

e Did you have a lot of energy? 1 2 3 4 5

f Have you felt downhearted and depressed? 1 2 3 4 5

g Did you feel worn out? 1 2 3 4 5

h Have you been happy? 1 2 3 4 5

i Did you feel tired? 1 2 3 4 5

10. During the past 4 weeks, how much of the time has your physical health or emotional problems interfered with your social activities (like visiting with friends, relatives, etc.)?

All of the time	Most of the time	Some of the time	A little of the time	None of the time
 1	 2	 3	 4	 5

11. How TRUE or FALSE is each of the following statements for you?

Definitely true	Mostly true	Don't know	Mostly false	Definitely false
				

- ^a I seem to get sick a little easier than other people 1 2 3 4 5
- ^b I am as healthy as anybody I know 1 2 3 4 5
- ^c I expect my health to get worse 1 2 3 4 5
- ^d My health is excellent 1 2 3 4 5

Thank you for completing these questions!

Table 16-6 FACT-Th6 (Version 4)

Below is a list of statements that other people with your illness have said are important. Please circle or mark one number per line to indicate your response as it applies to the past 7 days.

		Not at all	A little bit	Some- what	Quite a bit	Very much
An7	I am able to do my usual activities.....	0	1	2	3	4
Th3	I worry about problems with bruising or bleeding.....	0	1	2	3	4
Th4	I worry about the possibility of serious bleeding.....	0	1	2	3	4
Th10	I avoid or limit physical activity (because of concern with bleeding or bruising).....	0	1	2	3	4
Th11	I avoid or limit social activity (because of concern with bleeding or bruising).....	0	1	2	3	4

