Th12	I am frustrated by not being able to do my usual activities ..	0	1	2	3	4

Table 16-7 FACT-G (Version 4)Please circle or mark one number per line to indicate your response as it applies to the past 7 days.

PHYSICAL WELL-BEING		Not at all	A little bit	Some-what	Quite a bit	Very much
GP1	I have a lack of energy	0	1	2	3	4
GP2	I have nausea	0	1	2	3	4
GP3	Because of my physical condition, I have trouble meeting the needs of my family	0	1	2	3	4
GP4	I have pain	0	1	2	3	4
GP5	I am bothered by side effects of treatment	0	1	2	3	4
GP6	I feel ill	0	1	2	3	4
GP7	I am forced to spend time in bed	0	1	2	3	4
SOCIAL/FAMILY WELL-BEING		Not at all	A little bit	Some-what	Quite a bit	Very much
GS1	I feel close to my friends	0	1	2	3	4
GS2	I get emotional support from my family	0	1	2	3	4
GS3	I get support from my friends	0	1	2	3	4
GS4	My family has accepted my illness	0	1	2	3	4
GS5	I am satisfied with family communication about my illness	0	1	2	3	4
GS6	I feel close to my partner (or the person who is my main support)	0	1	2	3	4
Q1	Regardless of your current level of sexual activity, please answer the following question. If you prefer not to answer it, please mark this box  and go to the next section.					
GS7	I am satisfied with my sex life	0	1	2	3	4

Table 16-8 Treatment Satisfaction Questionnaire (TSQM)**Instructions:**

Please take some time to think about your level of satisfaction or dissatisfaction with the medication you are taking. We are interested in your evaluation of the effectiveness, side effects, and convenience of the medication *over the last two to three weeks, or since you last used it*.

For each question, please place a single check mark below the response that most closely corresponds to your own experiences.

1. How satisfied or dissatisfied are you with the ability of the medication to prevent or treat your condition?

Extremely Dissatisfied	Very Dissatisfied	Dissatisfied	Somewhat Satisfied	Satisfied	Very Satisfied	Extremely Satisfied
						
 1	 2	 3	 4	 5	 6	 7

2. How satisfied or dissatisfied are you with the way the medication relieves your symptoms?

Extremely Dissatisfied	Very Dissatisfied	Dissatisfied	Somewhat Satisfied	Satisfied	Very Satisfied	Extremely Satisfied
						

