2.7.4.2 FACT-Th6

There are 6 questions in FACT-Th6 questionnaires. The calculation of total score is done by multiplying the sum of the item scores by the number of items in the subscale, then divide by the number of items answered. This produces the subscale score. FACT-Th6 score will only be computed if we have no more than 2 missing responses.

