2.10.3 Functional Assessment of Cancer Therapy - Thrombocytopenia 6-item version (FACT-Th6) instrument is used to measure worry/concern about bleeding and bruising, and the impact of this worry/concern on physical and social activity (Cella 2006). FACT-Th6 is a 6-item subset of the more detailed FACT-Th, which is an 18-item subscale of the validated FACT that specifically measures concerns related to thrombocytopenia in the past 7 days. The FACT-Th6 is scored using a 5-level Likert scale (0=not at all to 4=very much) and is calculated by summing scores for the 6-items; therefore, scores can range from 0–24, with higher scores representing better HRQoL. No minimum clinically important change thresholds have been established for FACT-Th6. Tentatively anchor-based methods (e.g., based on Patient Global Impression of Change [PGIC] and Patient Global Impression-Severity [PGIS]) and distribution-based methods will be used to determine meaningful change in scores. FACT-Th6 demonstrated good reliability and validity for measuring the proposed constructs in the ITP population. Patients will be administered the FACT-Th6 at baseline, every 3 months during treatment, and EOT. Mean, SD, median, maximum, minimum, 25th and 75th percentile will be provided. Box plot at baseline, 3, 6, 9, 12, 15, 18, 21, 24 months and EOT will be provided. Descriptive statistics will be used to summarize change from baseline at month 3, 6, 9, 12, 15, 18, 21, 24 and EOT.

2.10.4 GP5, which is a single question, is used to assess the overall bothersomeness of treatment side effects. The GP5 is scored using a 5-point rating scale (0 = not at all; 1 = a little bit; 2 = somewhat; 3 = quite a bit; and 4 = very much), where lower scores reflect less bothersomeness from treatment side effects. The GP5 will be evaluated at baseline, 12 months, 24 months and EOT. The frequencies and percentages for each of the rating points will be provided.

Descriptive statistics will be used to summarize change from baseline to >0-3 months, >3-6 months, >6-9 months >9-12 months, >12 months and EOT. Shift table from baseline to worst post-baseline value will also be provided.

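### FACT-Th6 scoring in the SAP does not say which items are reversed, and on the item coding it states, none of the rules it gives yields a total where higher means better

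*SAP*

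**What the plan says.** Four places describe FACT-Th6 scoring.

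- **Protocol 8.5.1**: six items coded 0 to 4; the total "is calculated by summing scores for the 6-items", range 0–24, higher is better. No reversal is mentioned.
- **SAP 2.10.3**: the same. It gives the coding ("The FACT-Th6 is scored using a 5-level Likert scale (0=not at all to 4=very much"), a plain sum, the range 0–24 and the direction ("with higher scores representing better HRQoL"). No reversal is mentioned.
- **SAP 2.7.4.2**: a prorated total, obtained by "multiplying the sum of the item scores by the number of items in the subscale" and dividing by the number answered, with at most two items missing. No reversal is mentioned.
- **SAP 5.2**: "The total score is calculated by summing Th3+Th4+ Th10+ Th11 + Th12 and An7 after reversal". Reversal is mentioned, but the items it covers are not listed.

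The items are in protocol Table 16-6. Th3 ("I worry about problems with bruising or bleeding"), Th4, Th10, Th11 and Th12 (frustration "by not being able to do my usual activities") are negatively worded. An7 ("I am able to do my usual activities") is the only positively worded item.

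The other two quality-of-life instruments do have reversal rules. SAP 5.2 lists the SF-36v2 questions to be recoded. For FACIT-Fatigue it reverses all items except two, by subtracting the response from 4, and SAP 2.10.1 identifies the two exceptions as items 7 and 8.

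**The concern.** A scoring rule has to make each item push the total in the stated direction. On the stated coding, a high answer to a Th item is bad and a high answer to An7 is good. The total can therefore run from worst to best only if the five Th items are reversed and An7 is kept. Three places in the plan reverse nothing. The fourth uses wording that attaches reversal either to An7, the one item that should not be reversed, or to all six.

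FACT-Th6 change from baseline (months 3 to 24 and end of treatment) is part of secondary endpoint 7, and SAP 2.7.2 presents it by sustained-response status at month 12. If the wording was programmed literally on the stated coding, the reported change would be inverted or distorted. An inverted score would also invert the contrast between responders and non-responders.

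**Working it through.** **Inputs.** Responses are coded 0 to 4 (SAP 2.10.3, protocol 8.5.1). Item wording is from protocol Table 16-6. Reversal means 4 minus the response, as SAP 5.2 defines it for FACIT-Fatigue. Let *a* be the An7 response (0–4) and *t* the sum of the five Th responses (0–20). The best state is *a* = 4, *t* = 0; the worst is *a* = 0, *t* = 20.

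**Range and direction.**

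| Rule | Formula | Range | Best state | Worst state |
|---|---|---|---|---|
| Plain sum | a + t | 0–24 | 4 + 0 = 4 | 0 + 20 = 20 |
| Only An7 reversed | (4 − a) + t | 0–24 | 0 + 0 = 0 | 4 + 20 = 24 |
| All six reversed | (4 − a) + (20 − t) | 0–24 | 0 + 20 = 20 | 4 + 0 = 4 |
| Five Th reversed, An7 kept | a + (20 − t) | 0–24 | 4 + 20 = 24 | 0 + 0 = 0 |

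The plan's 0–24 range reproduces under every rule. Its direction reproduces only under the last. Scoring all 5^6 = 15,625 response patterns confirmed the ranges and these identities:

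- An7-only = 24 − coherent, an exact mirror image.
- Plain = 24 − all-six.
- All-six − coherent = 4 − 2a, from −4 to +4 points.

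**Change from baseline.** Let *T* be the fall in *t* (net improvement on the Th items) and *A* the rise in *a*. The change scores are:

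- coherent: T + A
- all six reversed: T − A
- only An7 reversed: −(T + A)
- plain sum: A − T

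| T | A | Coherent | All six | An7 only | Plain |
|---|---|---|---|---|---|
| +10 | +1 | +11 | +9 | −11 | −9 |
| +1 | +2 | +3 | −1 | −3 | +1 |
| +1 | −2 | −1 | +3 | +1 | −3 |

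For all-six reversal, (T + A)(T − A) = T² − A², so the sign is opposite to the coherent one exactly when |A| > |T|. Since |A| is at most 4, this needs |T| of 3 or less. When |A| = |T| and both are non-zero, a real change is reported as zero or a null change as non-zero. With complete data the all-six error in a change score is −2A, at most 8 points either way.

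**Proration.** With An7 answered and 0, 1 or 2 Th items missing, the largest all-six error in a single score is 4, 4 × 6/5 = 4.8, or 4 × 6/4 = 6.0. With An7 missing, all-six equals coherent. An7-only stays at 24 − coherent throughout.

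**The opposite base coding.** If items were first stored with 4 for not at all, reversing only An7 gives (4 − (4 − a)) + (20 − t) = a + (20 − t), which is the coherent score in all 15,625 patterns. SAP 2.10.1 describes that coding for FACIT-Fatigue. SAP 2.10.3 states the reverse for FACT-Th6.

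**The case against.** The strongest reply is that the intent can be recovered. The 0–24 range, the stated direction and the item wording together leave only one of the four rules. An7 is also item 8 of FACIT-Fatigue (protocol Table 16-4), where the SAP already treats it the opposite way from the negative items. On the FACIT-Fatigue coding in SAP 2.10.1, reversing An7 alone is correct. The phrase in SAP 5.2 could also be shorthand for reversing whatever needs it, as SAP 2.7.4.1 directs for FACIT-Fatigue.

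This is a plausible account of where the wording came from, but it does not rescue the text. The general rule is stated only for FACIT-Fatigue, and SAP 2.10.3 gives FACT-Th6 the coding under which reversing An7 is wrong. SAP 5.2 itself describes FACIT-Fatigue on that same 0-to-4 coding and reverses all but two items. An7 therefore stays as answered in one paragraph and sits beside the reversal instruction in the next.

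Other parts of the reply stand. The failures are unequal: all-six reversal keeps the overall direction (20 against 4) and goes wrong only through An7, whereas the plain sum and An7-only reversal invert the ends of the scale. The endpoint is descriptive, is one of three instruments, and has no established threshold for important change. Derivations are held in a separate programming specification, so the program may well be right.

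**Conclusion.** The concern holds. On the stated coding, the plain sum and both readings of the reversal sentence contradict the plan's own direction for the score. If the program followed the text, the result would be an exact mirror image (An7 alone), a total whose extremes run the wrong way (plain sum), or a score off by up to 4 points and a change score off by up to 8 of 24 (all six, complete data).

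This rests on the item coding in SAP 2.10.3 being the one actually stored and on the item wording in protocol Table 16-6. What was programmed is not visible, and no output is shown to be wrong. Secondary endpoint 7 is affected; the primary endpoint is not. It should be corrected because the error would pass a range check and costs almost nothing to remove.

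**What to change.** Replace the FACT-Th6 sentence in SAP 5.2 with an explicit rule: on the coding 0 for not at all to 4 for very much, Th3, Th4, Th10, Th11 and Th12 are reversed (4 minus the response); An7 is not reversed; the six values are summed, and prorated after reversal if no more than two are missing; range 0–24, higher is better. Add one sentence each to SAP 2.7.4.2 and 2.10.3 so that they agree.

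Then check the derivation program, including the base coding in which the items are stored. The primary report was already final at this SAP version, and the version precedes the final database lock, so the check should cover both reports. The cost is three sentences and one program check. Outputs need correcting only if the check finds a rule other than the coherent one.
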